10.6.3.2 Analysis of Secondary Efficacy Endpoints

- Percent change from Baseline at the primary analysis time point in fasting apoC-III, TC, LDL-C, HDL-C, non-HDL-C, VLDL-C, apoB, and apoA-I will be compared between each ISIS 678354 treatment group and pooled placebo group using an ANCOVA model with baseline as covariate
- Proportion of patients who achieve fasting TG ≤ 150 mg/dL (≤ 1.7 mmol/L) at the primary analysis time point will be compared between each ISIS 678354 treatment group and pooled placebo group using a logistic regression model with Baseline TG as a covariate. Proportion of patients who achieve fasting TG ≤ 100 mg/dL (≤ 1.13 mmol/L) at the primary analysis time point will be analyzed similarly

All analyses of secondary endpoints will be performed on the FAS as primary and PPS as supportive.

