This document provides a description of the statistical methods and procedures to be implemented for the analyses of data from the Akcea Therapeutics, Inc. study with Protocol Number ISIS 678354-CS2. The analyses described in this statistical analysis plan (SAP) are based upon the following study documents:

- Study Protocol, Amendment 3 (June 12, 2019)
- electronic Case Report Form (eCRF), Version 6.0 (March 06, 2019)

Section 1 discusses study design, objectives, and endpoints; Section 2 provides the study procedures; and, Section 3 provides the detailed plan for the statistical analyses. Any deviations from the final version of this Statistical Analysis Plan will be substantiated by sound statistical rationale and will be documented in the final clinical study report.

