2.4 Data Monitoring

In order to ensure maintenance of the study blind, the results of efficacy parameters consisting of lipid panel results including apoA-I, apoB, apoC-III, TC, LDL-C, HDL-C, non-HDL-C, VLDL-C, triglycerides, ANGPTL3 and Lp(a) will be blinded to the Akcea study team, Clinical Research Organization (CRO) study team, Investigators, Study Center personnel and patients until after database lock for EoT. After Sponsor's unblinding post completion of treatment period, blinded study personnel will continue to oversee the study until all patients completed the study.

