3 ANALYSIS PLANS

3.1 Statistical Design Summary

This is a multi-center, randomized, double blind, placebo-controlled study.

The study hypotheses will be formally evaluated at the planned EoT analysis on data obtained through the data cut-off date, defined as the date of the last EoT visit. The database will be queried, and data cleaning performed on all data, with database interim lock of all data, at which point the treatment code is unblinded and the EoT analysis is performed.

The primary analysis model will be an Analysis of Covariance (ANCOVA) model for percent change from baseline to the PAT in fasting triglycerides. Missing data will be imputed by a multiple imputation method as the primary analysis and will be supported by various sensitivity analyses.

The treatment groups proposed in this analysis are defined as follows:

- ISIS 678354 10 mg every 4 weeks (Q4W)
- ISIS 678354 50 mg every 4 weeks (Q4W)
- ISIS 678354 15 mg every 2 weeks (Q2W)
- ISIS 678354 10 mg every week (QW)
- Pooled Placebo, defined as the combined group of placebo patients from the 4 randomized cohorts

A final analysis will be performed after all data from the 13-week post treatment follow-up period are collected and locked.

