3.3.2 Primary Efficacy Analysis

The primary efficacy analysis for the primary endpoint will be the pairwise comparison of percent change from baseline to the primary analysis time point in fasting triglycerides between ISIS 678354 treated groups and pooled placebo group in the FAS.

The percent change from baseline in triglycerides will be analyzed using an ANCOVA model with treatment group as a fixed factor and log-transformed baseline triglycerides as a covariate. The ANCOVA model will use $\log(Y/X)$ as dependent variable, where Y is the post-baseline value of triglycerides and X is the baseline value of the triglyceride. The model will provide an estimate of the log ratio, which will then be converted back to the original ratio scale. The percent change from baseline will then be estimated based on the estimated ratio. Patients with missing primary endpoint will have their fasting triglyceride value imputed using the multiple imputation method described below.

Missing data for the primary efficacy endpoint will be handled by a multiple imputation model that contains the following variables: log-transformed baseline fasting triglyceride value, log-transformed fasting post-baseline triglyceride values, stratified by treatment ([Schafer 1997](#); [Schafer 1999](#)). Imputation of missing data will be conducted under a working assumption of missing at random (MAR), meaning that the propensity for a data point to be missing is not related to the missing data, but it is related to some of the observed data.

The imputations will be performed for post-baseline visits. The Markov Chain Monte Carlo (MCMC) method will be used under the multivariate normality assumption to impute the missing primary endpoint by treatment group (ISIS 678354 treatment group or pooled placebo treatment group). In order to be compliant with the normality assumption, baseline and post-baseline triglyceride data will be log-transformed prior to the imputation process and will be reverted when creating the imputed dataset. The MCMC method will impute 100 datasets in order to estimate the treatment effect, where the median value across the imputed datasets will be used for patients with missing endpoint.

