The primary endpoint will be compared between each ISIS 678354 treatment group and the pooled placebo group for each of the 100 imputed datasets. The estimates from the 100 fitted models will be combined to provide an overall estimate, with corresponding CIs and p-value ([Little and Rubin, 2002](#)). Results from the ANCOVA model will be tabulated by ISIS 678354 treatment groups compared to the pooled placebo group.

For fasting triglycerides, observed value, change from baseline and percentage of change will be summarized by analysis visit using descriptive statistics in FAS.

Mean (SD) percent change over time in fasting triglycerides will be plotted by ISIS 678354 treatment group and pooled placebo group, until there are fewer than 10% of the FAS/PPS population at a given visit. Waterfall plots of by-patient percent changes from baseline to the primary analysis time point will also be provided.

The primary efficacy analysis will take place after the last patient has completed the primary analysis time point, and the database has been locked.

All primary efficacy data will be provided in data listings.

The sample SAS code for the ANCOVA model can be found below: where the baseline and post-baseline values will be log-transformed first. Log (post-baseline/baseline) calculated as log (post-baseline) – log (baseline) will be subjected to the ANCOVA model.

* Note:

* Base= baseline

* Y=Post-baseline

* TRTP = Treatment group: Pooled Placebo, 10 mg Q4W, 50 mg Q4W, 15 mg Q2W, 10 mg QW

ods output lsmeans=lsm diff=diff;

proc mixed data = dataset;

 class TRTP (ref='pooled placebo') ;

 model log (Y/base) = TRTP log(Base) /solution cl;

 lsmeans TRTP/ diff cl;

run;

3.3.3 *Sensitivity Analyses of Primary Endpoint*

In addition to the primary efficacy analysis, the following sensitivity analyses will be conducted on the FAS.

Sensitivity Analysis 1 (Per Protocol Set): The primary efficacy analysis will be repeated, using the PPS population.

Sensitivity Analysis 2 and 3 (Non-Parametric Analyses): The primary efficacy endpoint will be analyzed using a non-parametric Wilcoxon Rank Sum test using both the FAS and the PPS. Missing data will be handled using the same MCMC multiple imputation method as the primary analysis. The

treatment effect will be estimated using the Hodges-Lehmann estimator of the location shift between ISIS 678354 treatment groups and the pooled placebo group. Asymptotic 95% CI and corresponding p-values will be provided.

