3.4 Secondary Efficacy Analyses

All analyses of secondary endpoints will be performed on the FAS as primary and PPS as supportive. Secondary efficacy analyses are based on the data collected at the primary analysis time point.

- Percent change from baseline at the primary analysis time point in fasting apoC-III, TC, LDL-C, HDL-C, non-HDL-C, VLDL-C, apoB, and apoA-I will be compared between each ISIS 678354 group and pooled placebo group using an ANCOVA model with log-transformed baseline as covariate. The ANCOVA model without applying any imputation for missing data will use $\log(Y/X)$ as dependent variable, where Y is the post-baseline lipid value and X is the baseline lipid value.
- Proportion of patients who achieve fasting triglycerides ≤ 150 mg/dL (≤ 1.7 mmol/L) at the primary analysis time point with MCMC imputation will be compared between each ISIS 678354 treatment group and pooled placebo group using a logistic regression model with baseline triglycerides as a covariate.
- Proportion of patients who achieve fasting triglycerides ≤ 100 mg/dL (≤ 1.13 mmol/L) at the primary analysis time point with MCMC imputation will be compared between each ISIS 678354 treatment group and pooled placebo group using a logistic regression model with baseline triglycerides as a covariate.

Summary statistics of the observed value, change and percent change from baseline by analysis visit will be performed for fasting apoC-III, TC, LDL-C, HDL-C, non-HDL-C, VLDL-C, apoB, and apoA-I on FAS.

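### The triglyceride responder analyses have no method for an empty placebo cell, which is likely at 100 mg/dL with about 20 patients per group

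*Combined protocol and SAP*

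**What the plan says.** SAP 3.4 defines two responder endpoints at the primary analysis time point, triglycerides at most 150 mg/dL and at most 100 mg/dL. Each "will be compared between each ISIS 678354 treatment group and pooled placebo group using a logistic regression model with baseline triglycerides as a covariate". Protocol 10.6.3.2 has the same plan for the 150 mg/dL endpoint, which "will be compared between each ISIS 678354 treatment group and pooled placebo group using a logistic regression model with Baseline TG as a covariate", and says the 100 mg/dL endpoint is handled similarly.

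Neither document says whether the test is Wald, score or likelihood ratio. Neither names a penalised or exact method, or a fallback for a zero cell. The model column of SAP Table 5 lists only ANCOVA for secondary endpoints.

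The endpoint text brings in imputation: "Proportion of patients who achieve fasting triglycerides ≤ 100 mg/dL (≤ 1.13 mmol/L) at the primary analysis time point with MCMC imputation". Section 3.4 does not say how the imputed data enter the logistic model. The only combining procedure is in SAP 3.3.2, written for the primary endpoint: "The estimates from the 100 fitted models will be combined to provide an overall estimate, with corresponding CIs and p-value". That section also has a sentence that points another way, "where the median value across the imputed datasets will be used for patients with missing endpoint". Section 3.4 does not say which applies to responder status, or whether one five-group model or four pairwise models are fitted.

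**The concern.** Patients enter with triglycerides of 200 to 500 mg/dL, so a placebo patient must roughly halve the value to reach 100. Some analysed baselines will be below 200, because SAP 3.2.4 averages two measurements and Protocol 5.1 allows a retest from 150. Even so, with about 20 placebo patients, zero responders is a foreseeable result.

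With an empty placebo cell the group effect is separated, and none of the four odds ratios against placebo has a finite maximum-likelihood estimate. What the software then prints depends on the test used and on where the iterations stop.

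Timing makes this matter. Under SAP 2.4 the lipid results "will be blinded to the Akcea study team, Clinical Research Organization (CRO) study team, Investigators, Study Center personnel and patients until after database lock". SAP 3.1 describes the interim lock, "at which point the treatment code is unblinded and the EoT analysis is performed". The empty cell would therefore be found with treatment assignment in view, and a test chosen then is chosen knowing which answer it gives.

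**Working it through.** **Group sizes.** About 25 patients per cohort (Protocol 3.3), randomised 4:1, gives 25 × 4/5 = 20 active per regimen. Pooled placebo is 4 × 5 = 20. The visible text gives no power figure for these endpoints, so there is nothing to reproduce.

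**When the cell is empty.** P(0/20) = (1 − p)^20. This exceeds 50% when p < 1 − 0.5^(1/20) = 3.4%.

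The documents give no placebo rate, so a range was simulated. The 36 scenarios cross median triglycerides 230/270/310 mg/dL, SD of the log ratio to baseline 0.25/0.35/0.45/0.55, and placebo drift 0/−10/−20%. Underlying log triglycerides were taken as normal with SD 0.3, and the entry, retest and baseline-averaging rules were applied.

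- At 100 mg/dL, P(0/20) runs from 19% to 99.9%. It is above 50% in 30 of 36 scenarios, and in all 12 with no drift.
- At 150 mg/dL it runs from 0.2% to 86%, and is above 50% in 5 of 36.
- A second grid, with simpler entry rules and SDs up to 0.60, gives 42 of 63 at 100 mg/dL and 5 of 63 at 150.

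**Why Wald fails.** With fitted placebo probability p0, the log odds ratio is logit(p1) − logit(p0), and its SE is √[1/(20·p1·q1) + 1/(20·p0·q0)], where q = 1 − p. Fitting drives p0 to zero. For 12/20 v 0/20:

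- p0 = 10⁻⁶: (0.405 + 13.816)/√(0.208 + 50,000) = 14.22/223.6 = 0.064, p = 0.95.
- p0 = 10⁻⁸: 18.83/2,236 = 0.008, p = 0.99.

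The SE grows much faster than the estimate, so p tends to 1 whatever the active count.

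**The same data under different tests** (no covariate, 0/20 on placebo):

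| Active | Wald | Likelihood ratio (LR) | Firth penalised LR | Fisher | Firth Wald |
|---|---|---|---|---|---|
| 4/20 | near 1 | 0.014 | 0.043 | 0.106 | 0.123 |
| 5/20 | near 1 | 0.006 | 0.018 | 0.047 | 0.085 |
| 6/20 | near 1 | 0.002 | 0.008 | 0.020 | 0.059 |
| 12/20 | near 1 | <0.0001 | 0.00001 | 0.00005 | 0.008 |

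**Type I error**, by exact enumeration of all 21 × 21 outcomes. Unpenalised LR: 2.9% at a common rate of 3.4%, 5.4% at 5%, 8.0% at 7.5% and 8.5% at 10%. Penalised LR: at most 5.0% at every rate from 0.5% to 50%.

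**Power.** Central set: median 270, no drift, SD 0.25/0.35/0.45, baseline as covariate, 1,500 trials per scenario. P(0/20) on placebo is 99.8/97/85% at 100 mg/dL and 77/45/23% at 150. Protocol 2.4 predicts reductions of about 30% to 64%.

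| Threshold, reduction | Wald | Penalised LR | Fisher | Firth Wald |
|---|---|---|---|---|
| 100, 64% | 0.1/3/15% | 99.5/99.6/99% | 99/98.5/98% | 96/94/94% |
| 100, 50% | 0/0.1/2% | 18/39/53% | 8/25/40% | 2/8/18% |
| 150, 64% | 19/50/75% | 100% | 100% | not tabulated |
| 150, 30% | 2/8/16% | 36/37/38% | 22/26/28% | 8/15/20% |

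At 100 mg/dL with a 30% reduction, Wald has 0% and penalised LR 0 to 2.5%.

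**With imputation** (10% missing, 30 imputations, 300 trials, Monte Carlo SE up to 3 points), at 100 mg/dL and 64% reduction: Rubin-pooled maximum-likelihood Wald 0/2/11%, pooled penalised profile likelihood 100/99/100%.

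**The case against.** The strongest reply is that the SAP never says Wald. The combining step in SAP 3.3.2 is written for the primary endpoint. If the median sentence applied instead, there would be one completed dataset and no pooling. That is right: the defect is an unspecified test, not a specified test that must fail. But section 3.4 offers no other procedure, and combining estimates with standard errors over the fits is Wald-type.

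A second reply defends the ordinary likelihood-ratio test. Where an empty cell is more likely than not, that test is conservative: its type I error is 0.2% at a 1% rate and 2.9% at 3.4%. Its excess appears at rates more relevant to 150 mg/dL. This stands as far as it goes. But the placebo rate is unknown and the size passes 5% once the rate reaches about 5%, so it is not a safe default for either endpoint.

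Third, the frequency rests on assumed grids. In the second grid, only 3 of the 18 scenarios with SD above 0.45 have an empty cell more likely than not. It is also true that at 5/20 and 6/20 the LR, penalised LR and Fisher tests all fall below 0.05. They first part at 4/20.

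Finally, the consequences are limited. Counts and percentages will be reported, so 12/20 v 0/20 would be visible whatever the p-value. The SAP also allows changes: "Any deviations from the final version of this Statistical Analysis Plan will be substantiated by sound statistical rationale". That permits a repair, but not one made blind to treatment.

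**Conclusion.** The concern holds. It is a pre-specification gap that should be closed, mainly for the 100 mg/dL endpoint. The missing method and the behaviour of each test at 0/20 follow from the design and need no assumption about the data. How often the cell is empty does depend on assumed variability and placebo drift: 30 of 36 scenarios in one grid, 42 of 63 in the other. The loss of power applies if Wald inference is used.

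At the upper predicted effect of 64%, central-set power at 100 mg/dL is 0.1 to 15% with Wald and 99% or more with penalised LR. For a 30% reduction no method has useful power at that threshold. The primary ANCOVA and the dose-selection criteria in Protocol 10.1.4 are not affected.

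**What to change.** In SAP 3.4, for both responder endpoints and before unblinding:

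1. Fit Firth penalised logistic regression with baseline triglycerides as covariate. Take the p-value and confidence interval from the penalised profile likelihood. Do not use Firth Wald, which is more conservative than Fisher at 100 mg/dL. This is still logistic regression with the covariate named in Protocol 10.6.3.2.
2. State that responder status is derived in each of the 100 imputed datasets, not from a median value, and state the pooling rule. One workable rule treats the signed root of the penalised LR as a function of the log odds ratio and averages its normal CDF over imputations. The 2.5% and 97.5% points give the interval, and twice the smaller tail at zero gives p. Rubin-pooled Firth Wald is simpler but weaker: 2/4/14% against 14/35/42% power at 100 mg/dL with a 50% reduction.
3. State one five-group model, as in the primary ANCOVA code, or four pairwise models. Power differs by at most 2 points, but the 5% decision for a single regimen can differ in up to 7% of trials.
4. Give Fisher's exact test on observed data, and risk differences with score or exact intervals, as support. State that unpenalised Wald and LR results will not be used for inference.
5. Add logistic regression to the secondary row of Table 5.

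The cost is SAP wording, one table entry, the Firth option and a small custom pooling step. The odds ratio is shrunk slightly, and the test is conservative at low responder rates (type I error about 0 to 3%). No patients or data are added.

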3.5 Exploratory Efficacy Analyses

All analyses of exploratory endpoints will be performed on the FAS. Percent change from baseline at the primary analysis time point in fasting Lp(a), remnant cholesterol, and ANGPTL3 as log-transformed ratio of post-baseline to baseline value will be compared between each ISIS 678354 group and pooled placebo group using an ANCOVA model with log-transformed baseline as covariate. Summary statistics including observed value, change and percent change from baseline by analysis visit will also be performed.

Table 5 outlines the analysis methods used in each efficacy analysis.

Table 5 Summary of Analysis Methods in Efficacy Analyses

Endpoint	Analysis Type	Log-Transformed Data	MCMC imputation	Population	Model
Primary Endpoint	Primary Analysis	Yes	Yes, assume MAR	FAS	ANCOVA
	Sensitivity Analysis 1	Yes	Yes, assume MAR	PPS	ANCOVA
	Sensitivity Analysis 2	Yes	Yes, assume MAR	FAS	non-parametric Wilcoxon Rank Sum test
	Sensitivity Analysis 3	Yes	Yes, assume MAR	PPS	non-parametric Wilcoxon Rank Sum test
	Sensitivity Analysis 4	Yes	Yes, Placebo: assume MAR. ISIS 678354: missing before discontinuation, assume MAR; missing after discontinuation assume CIR	FAS	ANCOVA
	Sensitivity Analysis 5	Yes	No	FAS	ANCOVA
	Sensitivity Analysis 6	Yes	No	FAS	MMRM
	Subgroup Analysis	Yes	Yes	FAS	ANCOVA
Secondary Endpoints	Secondary Analysis	Yes	Yes for triglycerides; No for other endpoints	FAS and PPS	ANCOVA
Exploratory Endpoint	Exploratory Analyses	Yes	No	FAS	ANCOVA

3.6 Pharmacokinetic and Anti-Drug Antibody analysis

3.6.1 Pharmacokinetic Data Analysis

All PK data analysis will be conducted using the PK Population except the listing of PK concentrations which will be conducted on the Safety Set.

The concentrations of ISIS 678354 in plasma expressed as ISIS 678354-equivalent (as total full-length oligonucleotides, including fully conjugated, partially conjugated, and unconjugated ISIS 678354) will be summarized by nominal visit by treatment group with and without stratification by patient ADA status using descriptive statistics. In addition, plasma terminal elimination half-life of ISIS 678354 will be calculated using the post-treatment follow-up data if data permits.

Additionally, for patients in the PK subgroup only, PK parameters will be calculated using non-compartmental methods. The maximum plasma concentration (C_{max}) and time to reach C_{max} (T_{max}) values will be obtained directly from the plasma concentration-time data. The area under the plasma concentration-time curve (AUC) values after the first dose (AUC_{0-24h}) and steady-state dose (AUC_{0-24h} and AUC_{tau}) will be calculated using the linear trapezoidal rule. Other PK parameters may be calculated at the discretion of the Sponsor. Plasma PK parameters will be summarized using descriptive statistics with and without stratification by patient ADA status.

Exposure-response relationships between selected lipid and PK measures (e.g., plasma trough concentrations) may be explored in a separate population PK/PD analysis combined with other clinical studies.

3.6.2 Anti-Drug Antibody Data Analysis

All ADA data analysis will be conducted using the Safety Set.

The ADA of ISIS 678354 will be assessed before, during, and after treatment with Study Drug (ISIS 678354 or placebo). The ADA incidence will be summarized by nominal visit and at the patient level by treatment group, as the total number of and percent of evaluated patients with ADA negative, positive, and unknown status. Patient ADA status (positive, negative or unknown) for all evaluable patients, along with the study day associated with the first emergence of ADA positivity (i.e., onset of ADA), the last positive ADA status observed, and peak ADA titer will be listed by treatment group. Potential relationships of ADA with selected efficacy, safety, and PK measures may be evaluated.

3.7 Safety Analyses

All safety analyses will use the Safety Set unless otherwise specified. Unless noted otherwise, denominators for all tables will be number of patients in the SS. Safety endpoints including laboratory assessments and vital signs will be analyzed by nominal visit collected on CRF.

Adverse events, concomitant medications, safety shift tables, and all tables related to safety monitoring/stopping rules will be summarized by 2 periods: on-treatment and on-study. On-treatment assessment is defined as the assessment from the first dose to the last dose of Study Drug plus one dosing interval. For Cohorts A and B, on-treatment period spans time from first dose to the last dose + 28 days; For Cohort C, on-treatment period spans time from first dose to the last dose + 14 days;

For Cohort D, on-treatment period spans time from first dose to the last dose + 7 days. On-study assessment is defined as the assessment from the first dose to the last visit in post-treatment follow-up period.

